### **7.3. Discontinuations**

#### **7.3.1. Discontinuation of Patients**

The criteria for enrollment must be followed explicitly. If the investigator site identifies a patient who did not meet enrollment criteria and who was inadvertently enrolled, the sponsor must be notified. If the sponsor identifies a patient who did not meet enrollment criteria and who was inadvertently enrolled, the investigator site will be notified. A discussion must occur between the sponsor's clinical research physician (CRP) and the investigator to determine whether the patient may continue in the study, with or without investigational product. Inadvertently enrolled patients may be maintained in the study and on investigational product when the Lilly CRP agrees with the investigator that it is medically appropriate for that patient. The patient may not continue in the study if the Lilly CRP does not agree with the investigator's determination that it is medically appropriate for the patient to continue. The investigator must obtain documented approval from the Lilly CRP to allow the inadvertently enrolled patient to continue in the study with or without investigational product.

In addition, patients will be discontinued from the study drug in the following circumstances:

- patient has evidence of symptomatic progression or confirmed objective progressive disease (radiological assessments by RECIST version 1.1). The important decision in determining whether a patient can continue on study drug should be based on his/her clinical symptoms, even if the patient has progressive disease based on radiological evidence. The investigator may also take into consideration biomarker responses, such as AFP elevations.
- enrollment in any other clinical trial involving an investigational product or enrollment in any other type of medical research judged not to be scientifically or medically compatible with this study
- investigator decision
  - The investigator decides that the patient should be discontinued from the study or study drugs. If this decision is made because of an SAE or a clinically significant

laboratory value related to the study drug, the study drug is to be discontinued, and appropriate measures are to be taken. Lilly or its designee is to be alerted immediately.

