**Table JBAS.9.2. Doses Adjustments for LY2157299**

Events Possibly Related to LY2157299	Adjustment
ANC <0.5 x 10  /L for longer than 7 days, or ANC <1.0 x 10  /L with a single temperature of >101°F/38.3°C or a sustained temperature of >100.4°F/38°C for >1 hour	LY2157299 will be omitted until the event resolves
Platelet count <25 x 10  /L	LY2157299 will be omitted until the event resolves
CTCAE Grade 3 or 4 nonhematologic toxicity	LY2157299 will be omitted until the event resolves

Abbreviations: ANC = absolute neutrophil count; CTCAE = Common Terminology Criteria for Adverse Events.

- Nonhematologic toxicity must resolve to CTCAE Grade 0, 1, or baseline level before resuming treatment (with the exception of alopecia, fatigue, skin rash, nausea, vomiting, constipation, or diarrhea that can be controlled with treatment).
- Hematologic toxicity must resolve to a level that, in the opinion of the investigator, is reasonable to allow for continuation of treatment.

If dosing is delayed for >2 weeks for treatment-related AEs, the patient should be withdrawn from the study treatment. Patients who do recover within the 2-week time frame may have the dosage reduced to 160 mg/day (or 80 mg/day if selected dose for the combination is 160 mg/day).

In case of a dose delay of LY2157299, patients can continue sorafenib treatment (at investigator discretion).

No patient will have his/her LY2157299 dose reduced more than once. Reescalation to the previous LY2157299 dose is acceptable in the absence of continuing or cardiac toxicities. If subsequent LY2157299 dose reduction is required after reescalation, the patient must be maintained at the reduced dose level for all remaining cycles.

If moderate or severe heart valve toxicities are observed, the patient must immediately be discontinued from the treatment (for definitions see [Attachment 14](#), including references on the echocardiographic assessment based on the Guidelines of the American and European Societies of Cardiac Echocardiography). Exceptions to this rule must be approved by the ERBs and Lilly.

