### 9.7. Treatment Compliance

Patient compliance with study medication will be assessed at each visit. Compliance will be assessed by direct questioning, review of diary, and counting returned tablets. Deviations from the prescribed dosage regimen should be recorded in the “Study treatment: modifications” form.

For patients who are significantly noncompliant (<80% or >120% of expected study drug taken in a visit interval), investigative sites must counsel patients on the importance of study drug compliance and drug accountability. Patients who are consistently out of the compliance range may be discontinued. A Lilly representative should be contacted upon the second instance of treatment noncompliance.

The following procedures will be employed to ensure appropriate drug accountability:

- Drug accountability will be emphasized at the start-up meeting.
- Drug accountability will be monitored throughout the study.
- Each patient should be instructed to return all study-drug packaging and unused material to the study site at each visit. The study site will keep a record of all drug dispensed to and returned by the patients throughout the study. Study site personnel will return or destroy (as requested) all unused study drug for all patients.

Patients will keep a study diary to document that they are taking LY2157299/  
LY2157299-matched placebo and sorafenib correctly.

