### 10.1. Efficacy Measures

All patients will be followed for progression and OS. Patients who come off therapy due to objective progressive disease will be followed for survival every 2 months. Patients may continue on study treatment even if they have objective progression or if they are clinically asymptomatic (see Section 7.3). However, it is important that the cycle response records

objective progressive disease in the cycle that it occurred in order to estimate TTP, PFS, and response rate without bias. These patients will then be discontinued from study treatment because of overall symptomatic deterioration (including biomarker response) or other causes. Patients who come off therapy and do not have objective progressive disease should be followed every 2 months after discontinuation from study treatment until death, including radiologic examinations every 6 weeks until objective progressive disease is determined (using the same radiological scans as at baseline). Patients who progress should then be followed for survival every 2 months. Every attempt should be made to gather all information every 2 months (radiological scans and survival), even if a patient starts a new anticancer therapy. Evaluation of survival can be accomplished by telephone contact if necessary. The date any new anticancer therapy starts, either during the 30-day safety or long-term follow-up periods, needs to be collected. This will enable a better estimate of time-to-event data to inform future decisions in this indication as it will be based on more mature data.

It is important that protocol procedures related to collection of these data, both during the active study treatment phase and follow-up period, are followed and that dates of data collection are recorded accurately.

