#### **10.3.2.2. Echocardiographs with Doppler and Chest Computed Tomography Scans**

Because of the cardiotoxicity monitoring in this study, echocardiographs with Doppler and chest CT scans are being performed (see [Attachment 1](#), [Attachment 14](#), and [Attachment 15](#)).

Echocardiography with Doppler will be locally assessed at screening for enrollment and throughout the study according to the Study Schedule ([Attachment 1](#)) for safety decisions by a physician or a person who is qualified by experience or training. The individual must be identified at each site. A central reading will be performed for the data used in the study report.

Chest CT scan with contrast of thorax and abdomen to evaluate the large vessels of the heart will be locally assessed at screening for enrollment and every 6 months throughout the study and at the end of study visit (Visit 801) according to the Study Schedule ([Attachment 1](#)) for safety decisions by a physician or a person who is qualified by experience or training. Alternatively, chest and/or abdomen MRI are allowed.

Chest CT scan with contrast of thorax and abdomen for tumor assessment will be locally assessed at screening for enrollment and every 6 weeks starting Cycle 2 Day 14 until radiological disease progression according to the Study Schedule ([Attachment 1](#)) by a physician or a person

who is qualified by experience or training. Alternatively, chest and/or abdomen MRI are allowed.

If the patient has clinically significant cardiac findings at discontinuation (Visit 801), echocardiography, ECG and ECG chemistry will be repeated every 2 months for 6 months (Visits 803, 804, and 805).

If there are no clinically significant cardiac findings at discontinuation (Visit 801), 1 more echocardiography, ECG, and ECG chemistry will be performed after 2 months (Visit 802). If a patient receives another treatment, Visit 802 cardiac assessments will not be performed.

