6.12.9. Protocol Violations

Significant protocol violations that potentially compromise the data integrity and patients' safety are listed by treatment group for all randomized patients.

Appendix 1 lists the categories of significant protocol violations, the detailed description of each violation within the category, and the method to identify each violation. Further details of study monitoring are in the Study Specific Monitoring Requirements (SSMR) document.

All data collected on the CRF will be checked programmatically for violations. Actual details specifying the programming methods will be given in the ADaM and table, figure, listing (TFL) specifications. Protocol violations that are documented in the monitoring database will be exported to an Excel file for import by statistics. Patients with significant violations may be excluded from the per-protocol population.

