Discontinuation criteria met but patient not removed from study (see Protocol Section 7.3.1)	Identified both by CRA during monitoring and programmatically: Discontinuation CRF data indicate criteria was met Lab data or the CRF AE page indicate that the subject was pregnant during the treatment. If echocardiography with Doppler data indicate moderate or severe heart valve toxicities are observed and patient is not removed from study.
Verify that the investigator has signed the CRF for all subjects who have screen failed, early discontinued, or completed the trial.	Identified both by CRA during monitoring and programmatically, if subject discontinued and Casebook Signature CRF is not completed.

Other	
Patient received drug that was declared “not Fit for Use”	Identified solely by CRA during monitoring.
Inadvertent un-blinding	Identified solely by CRA during monitoring.
Drug dispensing errors	Identified solely by CRA during monitoring.
Maintenance and calibration issues with critical equipment	Identified solely by CRA during monitoring. Verify maintenance and calibration records are current during the study for the following critical equipment: ECHO with Doppler Imaging Machines (CT/MRI) ECG If Applicable at site: DCE-MRI and/or DW-MRI Equipment needed to extract optional biopsy tissue
Other protocol violations that result in study discontinuation	As recorded on the CRF discontinuations page.

Abbreviations: AE = adverse event; CRA = clinical research associate; CRF = case report form; CT = computed or computerized tomography; DCE = Dynamic Contrast Enhanced; DW = diffusion weighted; ECG = electrocardiogram; ECHO = echocardiogram; MRI = magnetic resonance imaging.

Leo Document ID = b8cb3cf7-15b0-40a1-8f2d-8cd00cf2a27b

Approver: PPD

Approval Date & Time: 26-Jul-2017 01:50:30 GMT

Signature meaning: Approved

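### SAP Appendix 1 tests removal from the study where the protocol mainly stops study drug and then requires follow-up, so compliant patients can be listed as significant violators

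*SAP*

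**What the plan says.** **SAP.** In Appendix 1, Table 1, the category on violation of discontinuation criteria reads "Discontinuation criteria met but patient not removed from study (see Protocol Section 7.3.1)". It is identified by monitoring and by program. The named triggers are discontinuation case report form data, pregnancy, and echocardiography showing that "moderate or severe heart valve toxicities are observed and patient is not removed from study". Section 6.12.9 plans a listing of significant violations by treatment group for all randomized patients and adds: "Patients with significant violations may be excluded from the per-protocol population". Section 6.1.1 makes efficacy analysis in the per-protocol population optional and additional to the randomized population.

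**Protocol.** The list in Section 7.3.1 opens with the words "patients will be discontinued from the study drug in the following circumstances". For moderate or severe valve toxicity, Section 9.4.1.1 says "the patient must immediately be discontinued from the treatment"; exceptions are possible with ethics board and sponsor approval. Section 10.1 has patients who come off therapy followed for survival, with continued scans if they have not progressed. Section 10.3.2.2 adds that, after clinically significant cardiac findings at discontinuation, "echocardiography, ECG and ECG chemistry will be repeated every 2 months for 6 months".

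**The concern.** Stopping study drug and leaving the study are different events. The protocol mostly asks for the first and then keeps the patient under observation, because overall survival is the primary endpoint and cardiac safety needs follow-up. The Appendix 1 row tests for the second. Followed literally, it records a violation where the site did what the protocol asked.

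Two outputs are exposed. The violation listing, which is planned, could carry entries that are not violations and that hide the real ones. The per-protocol set, if used, could lose patients after randomization for conduct the protocol requires or permits.

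**Working it through.** No figure in the plan bears on this point and no arithmetic applies. The check sets the row against the protocol, case by case.

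| Patient | Under the protocol | Appendix 1 row as written |
|---|---|---|
| Meets a 7.3.1 criterion for stopping drug, stops, stays in survival follow-up | Compliant (7.3.1, 10.1) | Significant violation |
| Valve toxicity, drug stopped at once, followed at Visits 803 to 805 | Compliant (9.4.1.1, 10.3.2.2) | Significant violation |
| Valve toxicity, drug continued under an approved exception | Compliant (9.4.1.1) | Significant violation |
| Valve toxicity, drug continued with no approved exception | Not compliant | Significant violation |
| Study exit called for under 7.3.1, patient kept in the study | Not compliant | Significant violation |

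The row returns the same answer for the three compliant cases and the two that are not, so it does not discriminate. It also gives no time by which removal is expected.

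**Could *study* be shorthand for *study treatment*?** The SAP's own usage makes that hard to sustain.
- Section 6.5 documents discontinuation from treatment and from the study as two events, each with its reason.
- The dose-reduction row of Appendix 1 speaks of withdrawal from LY2157299 when it means the drug.
- Table JBAS.6.1 has long-term follow-up run until death to collect survival data.
- For extension-period patients with cardiac findings, Section 6.12.7 keeps the patient in the study beyond the 30-day visit.

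The safety-assessment row of Appendix 1 also makes scheduled assessments that were not done a significant violation. Read literally, a site with a valve-toxicity patient is flagged for keeping the patient in follow-up under one row, and for missing the follow-up echocardiograms under the other.

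**The criteria the row points to are not settled either.**
- *Progression.* Section 7.3.1 lists confirmed objective progression as a ground for stopping drug, yet the same bullet lets clinical symptoms decide. Section 10.1 says "Patients may continue on study treatment even if they have objective progression or if they are clinically asymptomatic". The synopsis describes treatment until the disease has progressed.
- *Noncompliance.* Section 7.3.1 lists significant noncompliance as a ground for stopping. Section 9.7 attaches that label to taking less than 80% or more than 120% of expected drug in a visit interval, asks for counseling, and then says: "Patients who are consistently out of the compliance range may be discontinued".

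These are tensions within the protocol. They matter here because the row takes its meaning from Section 7.3.1.

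**The case against.** The strongest reply is that this is a wording slip with little consequence. Much of that stands. Appendix 1 is an identification list; it does not itself exclude anyone. Exclusion is discretionary, the per-protocol analysis is optional, and efficacy analyses other than tumor response, including the primary survival comparison, use the randomized population. A sensible monitor would probably read the row in the light of Section 7.3.1. None of this makes the row correct: the listing is planned whether or not a per-protocol analysis is run, and the SAP elsewhere keeps the two events apart.

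It also stands that Section 7.3.1 is not solely about study drug. An inadvertently enrolled patient may have to leave the study, and the investigator, patient and sponsor decisions can end participation. A correction that mentions only study drug would miss those exits.

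Two further limits hold. Progression is not a named program trigger, so a patient treated past radiological progression would be found mainly by monitoring, and Section 7.3.1 gives the monitor grounds to treat that patient as compliant. Patients outside the 80% to 120% range in a cycle are already listed under a separate Appendix 1 row, so the discontinuation row adds little for them.

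**Conclusion.** The point holds in a limited form. The Appendix 1 row tests the wrong event for most of the criteria it cites, so patients who stop drug and stay in required follow-up meet its definition of a significant violation. The planned listing is affected directly. The per-protocol set is affected only if that analysis is run and the discretion to exclude is used. The primary survival analysis is not affected. This rests on reading the row as written.

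A reader might infer more, and the documents do not support it:
- *That a large or stated number of patients would be excluded.* The documents give no rate of treatment past progression, valve toxicity or approved exceptions, and no rule for when the discretion to exclude is used. The number cannot be derived.
- *That the row encourages sites to end survival follow-up.* Follow-up is required by the protocol, and nothing in Appendix 1 or SAP Section 6.12.9 overrides that.
- *That exclusions would differ by arm because Arm 1 is open label.* No passage says how often treatment past progression would occur in any arm.

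**What to change.** Change both Appendix 1 lines so that the violation is: a criterion was met and the action the protocol requires was not taken, meaning discontinuation of study drug or, where Section 7.3.1 calls for it, exit from the study. Do not flag valve-toxicity cases with an approved exception under Section 9.4.1.1. State that remaining in protocol-required follow-up after stopping drug is not a violation. Base the program on the treatment-discontinuation record, and on the study-discontinuation record only for study-level exits; SAP Section 6.5 already has both documented.

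Separately, reconcile the synopsis and Protocol Sections 7.3.1, 9.7 and 10.1 on progression and noncompliance, and make the check follow the reconciled text. Which clinical rule should apply is for the sponsor and investigators to settle.

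The cost is two reworded lines and one added sentence in the SAP appendix, a matching change to the programming specification, and a wording clarification in the protocol. No new data are needed.
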